### 10.7. Appendix 9: Study Schedule Supplement

#### 10.7.1. Screening (Day -7 [-3 days])

- Written informed consent and written documentation in accordance with the relevant country and local privacy requirements
- Demographic information
- Medical and ophthalmic histories
- Inclusion/exclusion criteria assessment
- Self-assessed surveys/questionnaires: Current Symptom Survey and OSDI Ouestionnaire
- Adverse event assessment
- Prestudy medication assessment
- Urine pregnancy test (for WOCBP only)
- Currently corrected distance visual acuity, BCVA, biomicroscopy, TBUT (with fluorescein), corneal staining (modified NEI grading, with fluorescein), conjunctival staining (modified NEI grading scheme, with lissamine green), Schirmer test (with anesthesia), and IOP (with anesthesia and fluorescein using a Goldmann applanation tonometer)
- Access IxRS
- Dispense run-in medication (if the patient meets the required Day -7 [Screening] qualifications)

Patients who fulfill all inclusion and exclusion criteria should be dispensed the run-in medication, REFRESH PLUS. They should be given instructions regarding the method of instillation and the dose regimen to be followed.

#### **10.7.2.** Baseline (Day 1)

- Inclusion/exclusion criteria assessment
- Medical and ophthalmic histories
- Concomitant medication assessment
- Adverse event assessment

- Self-assessed surveys/questionnaires: Study Eye Drop Usage Questionnaire, Current Symptom Survey, OSDI Questionnaire, and Functional Vision Questionnaire
- Currently corrected distance visual acuity, biomicroscopy, TBUT (with fluorescein), corneal staining (modified NEI grading, with fluorescein), conjunctival staining (modified NEI grading scheme, with lissamine green), Schirmer test (with anesthesia), and IOP (with anesthesia and fluorescein using a Goldmann applanation tonometer, only for participants with glaucoma or OHT)
- Monitor return of unused run-in medication and confirmation of run-in medication accountability
- Access IxRS
- Randomization
- Predose and postdose 5-Minute Blurry Vision and Ocular Discomfort Questionnaire
- Dispense study medication (if the participant qualifies for the study)

#### 10.7.3. Day 7 ( $\pm 3$ days)

- Self-assessed surveys/questionnaires: Study Eye Drop Usage Questionnaire, Current Symptom Survey, OSDI Questionnaire, Study Eye Drop Experience and Tolerability Questionnaire, and Functional Vision Questionnaire
- Adverse event assessment
- Concomitant medication assessment
- Currently corrected distance visual acuity, biomicroscopy, TBUT (with fluorescein), corneal staining (modified NEI grading, with fluorescein), conjunctival staining (modified NEI grading scheme, with lissamine green), Schirmer test (with anesthesia), and IOP (with anesthesia and fluorescein using a Goldmann applanation tonometer, only for patients with glaucoma or OHT)

#### 10.7.4. Days 30 and 60 ( $\pm$ 7 days)

- Self-assessed surveys/questionnaires: Study Eye Drop Usage Questionnaire, Current Symptom Survey, OSDI Questionnaire, Study Eye Drop Experience and Tolerability Questionnaire, and Functional Vision Questionnaire
- Adverse event assessment

- Concomitant medication assessment
- Currently corrected distance visual acuity, biomicroscopy, TBUT (with fluorescein), corneal staining (modified NEI grading, with fluorescein), conjunctival staining (modified NEI grading scheme, with lissamine green), Schirmer test (with anesthesia), and IOP (with anesthesia and fluorescein using a Goldmann applanation tonometer, only for patients with glaucoma or OHT)
- Monitor return of used and unused study intervention and confirmation of study intervention accountability
- Access IxRS
- Dispense study intervention

#### 10.7.5. Day 90/Early Exit (±7 days)

- Self-assessed surveys/questionnaires: Study Eye Drop Usage Questionnaire, Current Symptom Survey, OSDI Questionnaire, Study Eye Drop Experience and Tolerability Questionnaire, and Functional Vision Questionnaire
- Adverse event assessment
- Concomitant medication assessment
- Urine pregnancy test (for WOCBP only)
- Currently corrected distance visual acuity, BCVA, biomicroscopy, TBUT (with fluorescein), corneal staining (modified NEI grading, with fluorescein), conjunctival staining (modified NEI grading scheme, with lissamine green), Schirmer test (with anesthesia), and IOP (with anesthesia and fluorescein using a Goldmann applanation tonometer, only for patients with glaucoma or OHT)
- Access IxRS
- Predose and postdose 5-Minute Blurry Vision and Ocular Discomfort Questionnaire
- Monitor return of used and unused study intervention and confirmation of study intervention accountability

### 10.8. Appendix 10: Protocol Amendment History

The protocol amendment summary of changes table for the current amendment is located directly before the TOC.

#### Amendment 1 (February 2020)

This amendment is considered to be nonsubstantial based on the criteria set forth in Article 10(a) of Directive 2001/20/EC of the European Parliament and the Council of the European Union because it neither significantly impacts the safety or physical/mental integrity of participants nor the scientific value of the study.

#### **Overall Rationale for the Amendment:**

The overall rationale for the changes implemented in Protocol Amendment 1 is to remove the evaluation of a second new artificial tear formulation (NATF) formulation (011533X) from the study.

Section Number and Name	Description of Change	Brief Rationale
Title Page, Section 1 Synopsis, Figure 1-1, Section 2.1 Study Rationale, Section 2.2 Background, Section 2.3 Benefit/Risk Assessment, Section 3 Objectives and Endpoints, Section 4.1 Overall Design, Section 4.2, Scientific Rationale for Study Design, Section 6.1 Study Interventions Administered, Section 6.1.3 Instructions for Use and Administration, Section 6.3 Measures to Minimize Bias: Randomization and Masking, Section 6.4 Study Intervention Compliance, Section 9.1 Statistical Hypotheses, Section 9.4.1.4 Other Efficacy Analyses, Section 10.5 Appendix 5: Study Tabular Summary	Removed the NATF formulation 011533X arm from the study.	Administrative decision to focus development efforts and resources on a single formulation.
Section 1 Synopsis, Section 4.1 Overall Design, Section 5 Study Population, Section 9.2 Sample Size Determination, Appendix 5 Study Tabular Summary	Changed the total number of participants from approximately 600 to approximately 400 to be randomized in order to have 340 participants (170 participants in each arm) complete the study through Day 90, assuming an approximate 15% dropout rate.	Because the study is changing from a 3-arm to a 2-arm study, a smaller number of participants will be required.
Section 1 Synopsis, Section 4.1 Overall Design, Section 5 Study Population, Appendix 5 Study Tabular Summary	Changed the number of study sites from up to 40 sites to approximately 28 sites.	Because the study is changing from a 3-arm to a 2-arm study and a smaller number of participants will be required, a smaller number of sites will be required.

Section Number and Name	Description of Change	Brief Rationale
Section 5.1 Inclusion Criteria	Revised inclusion criterion 2.01 as follows: At the Screening (Day -7) and Baseline (Day 1) visits, at least 1 eye must qualify with both of the following ocular staining scores and the same eye must qualify at both visits:	For clarification.
Section 5.2 Exclusion Criteria	Added the following exclusion criterion 1.02: At the Screening (Day -7) or Baseline (Day 1) visits, one or both eyes have  • Corneal staining score of 5 in any of the 5 zones or a total score of <5 or > 19 based on the modified NEI grading scheme (score range = 0 to 5; graded in 5 zones of the cornea for a total score range of 0 to 25)  or  • Conjunctival staining score of 5 in any of the 6 zones based on the modified NEI grading scheme (score range = 0 to 5 per zone)	For clarification.
Section 8.1.3.2 Corneal Staining (Modified NEI Grading Scheme, with Fluorescein)	Revised the following text; Fluorescein staining will be evaluated using a slit-lamp with full slit width and approximately 10X to 16X magnification with cobalt blue illumination and a yellow barrier filter to enhance contrast.	For clarification.
Section 8.1.3.3 Conjunctival Staining (Modified NEI Grading Scheme, with Lissamine Green)	Revised the following text: Using the white light of low to moderate intensity, tThe 6 conjunctival regions (3 nasal and 3 temporal) will be graded using the modified NEI grading scheme (score between 0 and 5 per region) yielding a maximum possible score per eye of 30.	For clarification.

Section Number and Name	Description of Change	Brief Rationale
Section 9.1 Statistical Hypotheses	Revised the following text:  • H 0 : The NATF (011516X) is not noninferior compared to Systane Ultra MD as measured by the mean change from baseline in	For clarification.
Section 9.4.1.2 Primary Analyses	Revised the following text:  In order to control the overall type I error rate in the primary efficacy analysis, the Hoehberg Bonferroni reverse fixed sequences equential procedures will be used since performed.  Under this procedure, the mull hypotheses of noninferiority are nested in will be performed first and the mull hypotheses of superiority. Under this procedure, test will be performed next only if the null hypothesis of superiority is rejected using Hochberg test the null hypothesis of noninferiority is automatically rejected, and if the null hypothesis of noninferiority is tested using procedure the null hypothesis of noninferiority is tested using Bonferroni test. For each NATF tear formulation, test for superiority will be performed first by applying Hochberg's procedure at 0.05 significance level-rejected. To test the hypothesis of noninferiority, a 2-sided 97.595% confidence intervals interval will be constructed for the difference in the mean change from baseline in total staining at Day 90. If the upper limit of 2-sided CIsCI is less than 2.3 units, then the NATF tear formulation will be considered noninferior to Systane Ultra MD at the 2.3 unit margin. To test the hypothesis of superiority, a 2-sided test for superiority will be performed at the 0.05 significance level.	Because the study is changing from a 3-arm to 2-arm study, the primary analysis methods were updated.

1.0 Introduction

This statistical analysis plan (SAP) provides a technical and detailed elaboration of the statistical analyses of the efficacy and safety data as outlined and specified in the final Protocol 2007-301-005 Amendment 2 dated 08 Jun 2020. Specifications of tables, figures, and data listings are contained in a separate document.

2.0 Study Design and Objectives

2.1 Objectives and Hypotheses

The overall study purpose is to compare the efficacy and safety of a new artificial tear formulation (011516X) with Systane Ultra multidose in participants with dry eye disease (DED).

2.1.1 Objectives and Measures

Table 2-1 provides each objective and endpoint under the associated statistical analysis categories.

Objectives	Measures
Eff	icacy
	Primary Efficacy
To evaluate the efficacy of 011516X in participants with signs and symptoms of DED compared with Systane Ultra MD	Total staining (sum of corneal and conjunctival staining)
	Secondary Efficacy
	Current Symptom Survey
	Other Efficacies
	 Corneal staining (modified National Eye Institute [NEI] grading scheme, with fluorescein)
	 Conjunctival staining (modified NEI grading scheme, with lissamine green)
	• Tear break-up time (TBUT, with fluorescein)
	Schirmer test (with anesthesia)
	● Ocular Surface Disease Index [®] (OSDI)
	Study Eye Drop Experience and Tolerability Questionnaire
	Functional Vision Questionnaire

Table 2-1Objectives and Measures

abbyle 011516X: 2007-301-005 Statistical Analysis Plan

Version Amendment 1 - 2 August 2021

	5-Minute Blurry Vision and Ocular Discomfort Questionnaire
Saf	lety
To evaluate the safety of 011516X in participants with signs and symptoms of DED compared with Systane Ultra MD	 AEs Slit-lamp biomicroscopy Currently corrected distance visual acuity Best-corrected distance visual acuity (BCDVA) Intraocular pressure (IOP) (participants with glaucoma or ocular hypertension [OHT] only)

2.1.2 **Statistical Hypotheses**

The null and alternative hypotheses for the primary efficacy endpoint are:

Noninferiority

- H₀: µ011516X µSystane Ultra ≥2.3
- H_A: µ011516X µSystane Ultra < 2.3

Superiority

- H₀: $\mu_{011516X}$ $\mu_{Systane Ultra} \ge 0$.
- HA: µ011516X µSystane Ultra < 0 ٠

2.2 Study Design Overview

This study is designed as a multicenter, single-masked, randomized, 2-arm, parallel-group study comparing the efficacy and safety of a 011516X with Systane Ultra MD (see Figure 2-1). After a 7-days a run-in period, if still qualified at the Day 1 (Baseline) visit, participants will then be randomized in a 1:1 ratio to use 011516X or Systane Ultra MD. Participants will be instructed to instill 1 to 2 drops of their assigned study intervention (investigational eye drops) in each eye, 3 times per day for approximately 90 days. The

primary efficacy measure is total ocular staining and the primary analysis timepoint is at Day 90.

Approximately 400 participants (200 participants in each arm) will be enrolled at approximately 28 sites in the US in order to have 340 participants (170 participants in each arm) complete the study through Day 90, assuming an approximate 15% dropout rate. Participants who prematurely discontinue from the study will not be replaced.

No interim analyses are planned for this study.

2.2.1 **Schema**

The schematic of the study is shown in Figure 2-1.

2.3 **Treatment Assignment and Masking**

This study will use a 1:1 treatment allocation to 011516X or Systane Ultra MD, with a central stratification by Day 1 (Baseline) total ocular staining score in the study eye (mild/moderate = score of 6 to 25 vs severe = score of 26 to 43). The study eye is defined as the worst eye based on total ocular staining score at Day 1 (Baseline). If both eyes have the same total ocular staining score, the right eye will be designated as the study eye.

Prior to initiation of study intervention, each participant who provides informed consent will be assigned to a participant number through an automated IxRS that will serve as the participant's identification number on all study documents. Participant numbers will be assigned in ascending order across all sites and should not be omitted or reused.

At the end of the Screening (Day -7) visit, all eligible participants will receive a run-in medication kit (REFRESH PLUS) for use during the 7-day run-in period. Sites will dispense the run-in medication kit according to the IxRS instructions.

At the end of the Day 1 (Baseline) visit, all eligible participants will be stratified by their Day 1 (Baseline) study eye total ocular staining score and be randomly assigned to 1 of 2 treatment arms in a 1:1 ratio based on a randomization scheme prepared by Allergan Biostatistics. This will require the delegated site personnel to enter the participant's Screening Visit (Day -7) and Baseline (Day 1) total corneal and conjunctival staining scores of each eye directly into IxRS. IxRS will then determine which eye is the study eye and assign the participant to a stratification group and a treatment arm, thus providing the site with the specific study intervention kit assignment. Sites will dispense study intervention according to the IxRS instructions.

2.4 Sample Size Determination

The primary efficacy variable is change from baseline in total staining score at Day 90. Based on the assumption of noninferiority test for a between-group difference (ie, the

noninferiority margin) of 2.3 units in mean change from baseline in total staining at Day 90 with no inherent treatment difference with common standard deviation of 6.01, 170 participants will be required in each intervention group to detect the above intervention difference with a power of 90% or greater at the 1-sided 2.5% significance level. Assuming a 15% dropout rate, 200 participants will be randomized for each arm with a total of 400 participants to achieve the required sample size at Day 90.

3.0 Endpoints

3.1 **Primary Efficacy Endpoint**

The primary efficacy endpoint is defined as change from baseline in total staining score (sum of corneal and conjunctival staining scores) of study eye at Day 90.

3.2 Secondary Efficacy Endpoint

The secondary endpoint is defined as change from baseline in Current Symptom Survey total score (composite of all symptoms) at Day 90.

3.3 Other Exploratory Efficacy Endpoints

Other efficacy endpoints are listed below.

- Change from baseline in corneal staining score
- Change from baseline in conjunctival staining score
- Change from baseline in total staining score other than Day 90
- Change from baseline in Current Symptom Survey total score (composite of all symptoms) other than Day 90
- Change from baseline in individual symptom scores from Current Symptom Survey
- Change from baseline in Schirmer test
- Change from baseline in TBUT
- Change from baseline in OSDI
- Change from baseline in Functional Vision Questionnaire, 5-Minute Blurry Vision, and Ocular Discomfort Questionnaire
- Study Eye Drop Experience and Tolerability Questionnaire

Additional endpoints, such as responder proportions, can be added based on the study team requests.

3.4 Safety Endpoints

The safety variables include the study drug exposure, AEs, and results from the following assessments (Appendix B):

- Slit-lamp biomicroscopy
- Currently corrected distance visual acuity
- BCDVA
- IOP (participants with glaucoma or OHT only)

4.0 Analysis Populations

The analysis populations will consist of participants as defined below:

Population	Definition	Treatment Used for Analysis
Intent-to-treat (ITT)	Participants who are randomized	As randomized
Per-protocol (PP)	Randomized participants who have no protocol deviations affecting the primary efficacy analysis	As randomized
Safety	Treated participants who receive/take ≥ 1 administration of randomized study treatment	Actual received

Table 4-1Analysis Populations

Efficacy analyses will be done using the ITT population. Safety data analyses will be done using the safety population. The primary efficacy endpoint will also be done using for PP population.

Demographics and baseline characteristics will be done using the ITT population. Study drug duration, medical and surgical history, ophthalmic medical and surgical history, prior and concomitant medication will be done using the safety population.

The study eye is defined as the worst eye based on total ocular staining score at Day 1 (Baseline). If both eyes have the same total ocular staining score, the right eye will be designated as the study eye. The other eye will be the fellow eye.

5.0 Participant Disposition

Participant disposition encompasses the distribution of participants who enter the run-in period, get randomized, complete, and discontinue the 90-day randomized treatment period.

The summary of study disposition will be provided for the following:

- Number of participants in the run-in period
- Number of participants who fail to be randomized
- Number of participants randomized (this frequency count will be used as the denominator to calculate the percentages described below)
- Number and percentage of participants treated
- Number and percentage of participants who completed the study
- Number and percentage of participants who discontinued the study

6.0 Study Drug Duration

The study will consist of a 90-day treatment period. The treatment duration in days will be summarized using descriptive statistics by treatment group for the safety population.

The treatment duration will be calculated as last treatment date - first treatment date + 1.

The number and percentage of participants with each treatment duration (days) of ≥ 1 , ≥ 7 , ≥ 30 , ≥ 60 , and ≥ 90 will be summarized.

7.0 Demographics, Baseline Characteristics, Medical History, and Prior/Concomitant Medications

7.1 Demographics and Baseline Characteristics

Demographic parameters (age, sex, race, ethnicity) will be summarized descriptively by treatment group for the ITT population.

7.2 Medical and Surgical History

Medical and surgical histories will be collected at visits of screening and Day 1. They will be coded using the Medical Dictionary for Regulatory Activities (MedDRA), Version 23.0 or higher.

The number and percentage of participants with medical and surgical history in each primary system organ class and preferred term will be summarized by treatment group for the safety population.

7.3 **Ophthalmic Medical and Surgical History**

Ophthalmic medical and surgical histories will be collected at visits of screening and Day 1. They will be coded using the Medical Dictionary for Regulatory Activities (MedDRA), Version 23.0 or higher.

The number and percentage of participants with ophthalmic medical and surgical history in each system organ class and preferred term will be summarized by treatment group for the safety population.

7.4 Prior and Concomitant Medications

The medication data will be coded using the World Health Organization (WHO) Drug Dictionary Enhanced Version.

Prior medication is defined as any medication taken prior to the start of first randomized study treatment regardless of stop date of the medication. Concomitant medication is

defined as any medication taken on and after the start of first randomized study treatment regardless of the start date of the medication.

Prior and concomitant medications will be coded using the Anatomical Therapeutic Chemical code (4th level, or most specific level available if 4th level is unavailable).

The number and percentage of participants reporting prior or concomitant medications will be summarized further by ATC class and code, and preferred drug name. If more than one medication is coded to the same preferred drug name for the same participant, the participant will be counted only once for that preferred drug name. Prior and concomitant medications will be summarized by treatment group for the safety population, separately.

8.0 Efficacy Analyses

8.1 General Considerations

The following are general considerations for efficacy analyses:

- The efficacy analyses will be based on the ITT populations.
- Baseline is defined as the last non-missing assessment prior to the first dose of the single-masked study treatment.
- The change from baseline value will be computed as the postbaseline value minus the baseline value.
- Continuous variables will be summarized by number of participants with observed values (n), mean, standard deviation (SD), median, 1st and 3rd quartiles (Q1, Q3), minimum (min), and maximum (max).
- Categorical variables will be summarized by number of participants with observed values or events and percentages based on the specified population.
- All statistical analyses will be performed using SAS version 9.4 or higher.

8.2 Handling of Missing Data

Efficacy analyses will be based on observed data only.

8.3 Primary Efficacy Endpoint and Analyses

8.3.1 Primary Efficacy Endpoint

The primary efficacy variable is defined as the change from baseline in total staining score at Day 90.

8.3.2 Primary Efficacy Analysis

The primary efficacy analysis will be performed upon the ITT population using mixed effects repeated measures (MMRM) method. The difference and the 95% confidence interval will be constructed with the least squares means from the MMRM model with

treatment, visit, visit-by-treatment interaction, baseline total staining stratum, and baseline total staining stratum-by-visit interaction as the fixed effects. An unstructured covariance matrix will be selected for the repeated measure covariance.

In order to control the overall type I error rate in the primary efficacy analysis, the sequential procedures will be performed. Under this procedure, the noninferiority test will be performed first and the superiority test will be performed next only if the null hypothesis of noninferiority is rejected. To test the hypothesis of noninferiority, a 2-sided 95% confidence interval (CI) will be constructed for the difference in the mean change from baseline in total staining at Day 90. If the upper limit of 2-sided CI for the treatment difference (011516X minus Systane Ultra MD) is less than 2.3 units, then the 011516X tear formulation will be considered noninferior to Systane Ultra MD. If the upper limit of the aforementioned 2-sided CI is less than 0 units, then the 011516X tear formulation will be considered noninferior to Systane Ultra MD. Details of this procedure will be found in Section 12.0.

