## 4.2. Scientific Rationale for Study Design

This Phase 3 clinical study is designed to evaluate the efficacy and safety of the NATF 011516X versus a leading marketed artificial tear product, Systane Ultra MD, over a 90-day study intervention period in participants with DED.

The test formulation contains the same active ingredients (carboxymethylcellulose and glycerin) as the currently marketed REFRESH OPTIVE products. The solution also contains other inactive compatible solutes such as carnitine, erythritol, and trehalose.

The formulation of Systane Ultra MD incorporates hydroxypropyl-guar, and is currently the market leader.

The present study is designed to compare the relative relief of symptoms of DED between the formulations as well as to characterize the effect on ocular surface staining. In order to be able to show a reduction in DED symptoms and in ocular surface staining at Day 90, the inclusion criteria were selected to include a participant population with clinically significant ocular surface staining and symptoms of DED at the Screening (Day -7) and Day 1 (Baseline) visits. These participants are anticipated to have a clinically treatable condition with sufficient room for improvement.

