#### 9.4.1.2. Primary Analyses

The primary efficacy variable is the change from baseline in total staining score at Day 90.

The primary efficacy analysis will be performed in the ITT population using MMRM. The differences and the intervals will be constructed with the least squares means from the MMRM model with treatment, visit, visit by treatment interaction, and baseline total staining stratum, and baseline total staining stratum by visit interaction as the fixed effects. In order to control the overall type I error rate in the primary efficacy analysis, the sequential procedures will be performed. Under this procedure, the noninferiority will be performed first and the superiority test will be performed next only if the null hypothesis of noninferiority is rejected. To test the hypothesis of noninferiority, a 2-sided 95% confidence interval will be constructed for the difference in the mean change from baseline in total staining at Day 90. If the upper limit of 2-sided CI is less than 2.3 units, then the NATF tear formulation will be considered noninferior to Systane Ultra MD at the 2.3 unit margin. To test the hypothesis of superiority, a 2-sided test for superiority will be performed at the 0.05 significance level.

The primary efficacy variable will also be analyzed similarly on PP population as a sensitivity analysis.

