8.4 Secondary Efficacy Analyses

The secondary efficacy variable will be analyzed with the same model described for the primary efficacy analysis in Section 8.3.2. The difference and the 95% CI will be constructed.

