8.5 Exploratory Efficacy Analyses

Total staining score other than Day 90, Current Symptom Survey total score (composite of all symptoms) other than Day 90, individual symptom scores from Current Symptom

Survey, corneal staining score, and conjunctival staining score will be analyzed with the same method described for the secondary efficacy analysis in Section 8.3.2.

All other efficacy analyses will be performed to provide descriptive statistics. Summaries of the 011516X and Systane Ultra MD at each scheduled visit will be performed on Schirmer test, TBUT, Functional Vision Questionnaire, and Study Eye Drop Experience and Tolerability Questionnaire.

8.5.1 5-Minute Blurry Vision and Ocular Discomfort Questionnaire

The 5-Minute Blurry Vision and Ocular Discomfort Questionnaire will provide an assessment of blurry vision and ocular discomfort, each on a 0-100 scale. The assessment will be conducted at Day 1 and Day 90/Early Exit. At each visit, measurements will be collected before instillation of one drop to each eye (Baseline), and at post dose time points of 30 seconds, 1 minute, 90 seconds, 2 minutes, 3 minutes, 4 minutes, and 5 minutes. Change from baseline is calculated for each time point minus the pre-dose score of the same day.

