Appendix D. Changes to Protocol-planned Analyses

There are no changes from the protocol-planned analyses.

Electronic Signatures

User	Date	Justification
	02-Aug-2021 20:44:38 (GMT)	Document Originator Approval
	04-Aug-2021 19:44:44 (GMT)	NC - Study Director Approval
	02-Aug-2021 22:16:07 (GMT)	Subject Matter Expert Approval
	03-Aug-2021 21:36:05 (GMT)	Manager Approval

TITLE PAGE

Protocol 2007-301-005

A Multicenter, Single-masked, Randomized Study to Compare the Efficacy and Safety of a New Artificial Tear Formulation (011516X) with Systane[®] Ultra Multidose for 90 Days in Participants with Dry Eye Disease

PER-PROTOCOL ANALYSES DATA EXCLUSION ALGORITHM

Draft: 06-Aug-2021

Confidentiality Statement

Confidentiality Statement

This document is the property of AbbVie, Inc. and may not, in full or part, be passed on, reproduced, published, distributed to any person, or submitted to any regulatory authority without the express written permission of AbbVie, Inc. AbbVie Optive Super

HISTORY OF CHANGE

Amendment: Not applicable

Date	Description of Change(s)
06-Aug-2021	Initial version (Approved)

2007-301-005 Per-Protocol Analyses Data Exclusion Algorithm

1 Introduction

This document is written to detail the algorithms used to define data exclusions from the per-protocol analysis in the 2007-301-005 Amendment 2 and statistical analysis plan (SAP) Amendment 1.0.

The per-protocol (PP) population is defined in SAP section 4.0. The PP analysis will be implemented on the primary efficacy endpoint only. The PP population will consist of participants who contribute data to the PP analysis after implementing the data exclusion algorithms specified in this document. PP population will come from ITT population who are treated. Data from the participants with a protocol deviation that is deemed to affect primary efficacy assessment from a study visit will be excluded from the PP analysis for that study visit.

2 Algorithms to Define Data Exclusion for PP Analysis

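### The MMRM adjusts for baseline only through a two-level staining stratum and is reused for symptom endpoints, which costs precision but not validity

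*SAP*

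**What the plan says.** The primary outcome is change from baseline in study-eye total staining at Day 90 (SAP 3.1). SAP 8.3.2 models it with "treatment, visit, visit-by-treatment interaction, baseline total staining stratum, and baseline total staining stratum-by-visit interaction as the fixed effects", using an unstructured covariance matrix. Protocol 9.4.1.2 gives the same baseline terms: "baseline total staining stratum, and baseline total staining stratum by visit interaction as the fixed effects". The stratum has two levels, 6 to 25 and 26 to 43 (SAP 2.3).

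The secondary endpoint is "change from baseline in Current Symptom Survey total score (composite of all symptoms) at Day 90". SAP 8.4 states: "The secondary efficacy variable will be analyzed with the same model described for the primary efficacy analysis in Section 8.3.2". SAP 8.5 extends the approach to total staining and the Survey total at other visits, to the individual symptom scores, and to staining by site: "corneal staining score, and conjunctival staining score will be analyzed with the same method described for the secondary efficacy analysis". The remaining efficacy measures get descriptive statistics only, so this point does not reach them.

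Neither document adds a continuous baseline, or a baseline specific to the endpoint, to any model. Protocol 9.4.1.3 says only that the secondary variable is analysed by MMRM.

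**The concern.** The outcome is a change score, so its variance includes whatever part of the change the baseline value predicts. A split at 25/26 removes only some of that. Baseline differences that arise by chance within a stratum pass into the treatment difference unadjusted.

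The gap is wider for symptoms. The staining stratum need not predict symptom change at all, whereas the Survey score is collected on everyone at Day 1 and is the natural covariate. For corneal and conjunctival staining the stratum is a coarse proxy, because it is built from their sum.

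Two things are at stake: power at the superiority step, and the width of the symptom confidence interval. The symptom endpoint has no formal test (SAP 12.0), but Protocol 4.2 says "The present study is designed to compare the relative relief of symptoms of DED between the formulations". That interval is what readers will use.

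**Working it through.** **The plan's own figure.** Protocol 9.2 (margin 2.3, SD 5.98, 1-sided 1.25%, 90% power) gives 168 per arm by the normal formula and 170 by noncentral t. Then 170/(1 − 0.15) = 200 randomized. SAP 2.4 assumes a true difference of zero, "with no inherent treatment difference with common standard deviation of 6.01", at 1-sided 2.5%. Those inputs need 144 (normal) or 145 (t) per arm, and power at 170 is 94.0% (t) with no credit for any covariate.

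**Assumptions.** The documents do not give these, so ranges are used:
- correlation ρ between baseline and Day 90: 0.3 to 0.7
- SD ratio k (Day 90 SD / baseline SD): 0.8, 1.0 or 1.3
- share of participants in the severe stratum, p: 5% to 30%
- a normally distributed baseline, and 6.01 as the SD of change before covariate adjustment

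**Formulas.**
- Share of change variance explained by baseline: R² = (kρ − 1)² / (1 + k² − 2kρ).
- Part of that share captured by the stratum: c = φ(z)² / (p(1 − p)). At p = 5%, c = 0.1031²/0.0475 = 0.22. At p = 30%, c = 0.3477²/0.21 = 0.58.
- Primary SE ratio, baseline added against planned: √[(1 − R²)/(1 − cR²)].
- Symptom SE ratio, if the stratum explains none of the symptom change: √(1 − R²).
- Participant equivalent: 1/(SE ratio)² − 1.

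Example, k = 1, ρ = 0.5, p = 30%: R² = 0.25/1 = 0.25, and the SE ratio is √(0.75/0.856) = 0.936, a cut of 6.4%.

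| k | ρ | R² | Primary SE cut, 30% / 5% severe | Worth in participants | Symptom SE cut | Worth in participants |
|---|---|---|---|---|---|---|
| 0.8 | 0.3 | 0.50 | 16% / 25% | 42% / 77% | 29% | 99% |
| 0.8 | 0.5 | 0.43 | 13% / 20% | 32% / 58% | 24% | 75% |
| 0.8 | 0.7 | 0.37 | 11% / 17% | 25% / 46% | 21% | 59% |
| 1.0 | 0.3 | 0.35 | 10% / 16% | 23% / 42% | 19% | 54% |
| 1.0 | 0.5 | 0.25 | 6.4% / 11% | 14% / 26% | 13% | 33% |
| 1.0 | 0.7 | 0.15 | 3.5% / 6.2% | 7% / 14% | 8% | 18% |
| 1.3 | 0.3 | 0.195 | 5% / 8% | 10% / 19% | 10% | 24% |
| 1.3 | 0.5 | 0.088 | 2% / 4% | 4% / 8% | 4.5% | 10% |
| 1.3 | 0.7 | 0.009 | 0.2% / 0.4% | 0.4% / 0.7% | 0.5% | 1% |

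**Power** (noncentral t, 170 per arm, 1-sided 2.5%, ρ = 0.5):
- Noninferiority, k = 1: 95% to 97% with the planned model, 98% with baseline added.
- Superiority at an illustrative true difference of 1.5 units: from 0.66–0.70 to 0.755 at k = 1, and from 0.64–0.65 to 0.67 at k = 1.3.
- Superiority at 1.0 unit, k = 1: from 0.35–0.38 to 0.42.

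**Chance imbalance.** Under the planned model its SD is 6.01 × √(2/170) × √[R²(1 − c)] = 0.652 × √[R²(1 − c)]. At k = 1 this is 0.16 to 0.34 units, or 7% to 15% of the margin. It is part of the planned SE, not an added bias.

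**Validity.** In simulation (4000 stratified trials per case, ρ = 0.5, no true difference), the planned model's mean difference was within 0.03 of zero and one-sided type I error was 2.2% to 2.7%. Adding baseline took the empirical SE from 0.61–0.63 to 0.56–0.57 at k = 1, and from 0.62–0.64 to 0.61–0.62 at k = 1.3. A second simulation on a symptom scale (assumed SD 18, about 15% dropout) found bias near zero when dropout was unrelated to baseline or related to it equally in both arms. Bias of 0.3 to 2.0 points, with two-sided rejection of 5% to 14%, appeared only when dropout depended on baseline symptoms in opposite directions by arm. Adding baseline removed it.

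**The case against.** The planned model is valid, includes the stratification factor, and is the same in protocol and SAP. Noninferiority is powered above target without any covariate, and a wider interval is conservative there. The superiority gain rests on a true difference that the plan does not assume, and the symptom endpoint is outside the testing hierarchy. All of this stands, and it limits the point to one of efficiency.

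The size is also uncertain: the primary SE cut runs from 0.2% to 25% across the grid. Entry limits on baseline (corneal total 5 to 19, Survey score at least 25) tend to raise the SD ratio and lower the correlation, so a ratio of 1.0 has no special claim over 1.3. They also make the normal-baseline formula for c approximate. That stands too, but in none of the cells does adding baseline widen the SE.

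Finally, changing a primary model late, in a single-masked trial, is not trivial. SAP Amendment 1 is dated 2 August 2021, and the documents do not show whether the database had been locked. This is a condition on the fix, not a reason to leave the symptom models without their own baseline.

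**Conclusion.** The concern holds as a matter of precision. No planned decision is invalid, and the noninferiority conclusion is not at risk under the SAP's inputs. With equal SDs and correlations of 0.3 to 0.7, the plan gives up 3.5% to 16% of the primary SE and 8% to 19% of the symptom SE. With a Day 90 SD 1.3 times the baseline SD, the losses are 0.2% to 8% and 0.5% to 10%. The symptom figures assume that the staining stratum explains none of the symptom change. The claim of validity assumes that dropout does not depend on baseline in opposite directions in the two arms. The change should be made because the covariate is already collected and the likely gain is worth having for the superiority step and the symptom interval.

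**What to change.** Before database lock and unmasking:

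- In SAP 8.3.2, add the continuous Day 1 study-eye total staining score and its interaction with visit. Keep the stratum and its visit interaction.
- In SAP 8.4 and 8.5, specify the same model plus the continuous baseline of the endpoint being analysed and its interaction with visit. Protocol 9.4.1.3 lists no covariates, so this contradicts nothing there.
- Declare the departure from Protocol 9.4.1.2 in SAP Appendix D, which now reads "There are no changes from the protocol-planned analyses", or in a protocol amendment.

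If lock or unmasking has already happened, leave the primary model as planned and report the baseline-adjusted models as supportive analyses, labelled as added later.

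The cost is one covariate and its visit interaction per model, plus the declaration. Baseline is already needed to compute change, so no participants or data are lost.
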